8.3 Adverse Events and Serious Adverse Events

8.3.1 Definition of Adverse Events (AE)

Adverse event means any untoward medical occurrence associated with the use of an intervention in humans, whether or not considered intervention-related (21 CFR 312.32 (a)).

8.3.2 Definition of Serious Adverse Events (SAE)

An adverse event (AE) or suspected adverse reaction is considered "serious" if, in the view of either the investigator or sponsor, it results in any of the following outcomes: death, a life-threatening adverse event, inpatient hospitalization or prolongation of existing hospitalization, a persistent or significant incapacity or substantial disruption of the ability to conduct normal life functions, or a congenital anomaly/birth defect. Important medical events that may not result in death, be life-threatening, or require hospitalization may be considered serious when, based upon appropriate medical judgment, they may jeopardize the participant and may require medical or surgical intervention to prevent one of the outcomes listed in this definition. Examples of such medical events include allergic bronchospasm requiring intensive treatment in an emergency room or at home, blood dyscrasias or convulsions that do not result in inpatient hospitalization, or the development of drug dependency or drug abuse.

8.3.3 Classification of an Adverse Event

8.3.3.1 Severity of Event

For adverse events (AEs) not included in the protocol defined grading system, the following guidelines will be used to describe severity.

- **Mild** – Events require minimal or no treatment and do not interfere with the participant's daily activities.
- **Moderate** – Events result in a low level of inconvenience or concern with the therapeutic measures. Moderate events may cause some interference with functioning.
- **Severe** – Events interrupt a participant's usual daily activity and may require systemic drug therapy or other treatment. Severe events are usually potentially life-threatening or incapacitating. Of note, the term "severe" does not necessarily equate to "serious".

8.3.3.2 Relationship to Study Intervention

All adverse events (AEs) must have their relationship to study intervention assessed by the clinician who examines and evaluates the participant based on temporal relationship and his/her clinical judgment. The degree of certainty about causality will be graded using the categories below. In a clinical trial, the study product must always be suspect.

- **Definitely Related** – There is clear evidence to suggest a causal relationship, and other possible contributing factors can be ruled out. The clinical event, including an abnormal laboratory test result, occurs in a plausible time relationship to study intervention administration and cannot be explained by concurrent disease or other drugs or chemicals. The response to withdrawal of the study intervention (dechallenge) should be clinically plausible. The event must be pharmacologically or phenomenologically definitive, with use of a satisfactory rechallenge procedure if necessary.
- **Probably Related** – There is evidence to suggest a causal relationship, and the influence of other factors is unlikely. The clinical event, including an abnormal laboratory test result, occurs within a reasonable time after administration of the study intervention, is unlikely to be attributed to concurrent disease or other drugs or chemicals, and follows a clinically reasonable response on withdrawal (dechallenge). Rechallenge information is not required to fulfill this definition.
- **Potentially Related** – There is some evidence to suggest a causal relationship (e.g., the event occurred within a reasonable time after administration of the trial medication). However, other factors may have contributed to the event (e.g., the participant's clinical condition, other concomitant events). Although an AE may rate only as "possibly related" soon after discovery, it can be flagged as requiring more information and later be upgraded to "probably related" or "definitely related", as appropriate.
- **Unlikely to be related** – A clinical event, including an abnormal laboratory test result, whose temporal relationship to study intervention administration makes a causal relationship improbable (e.g., the event did not occur within a reasonable time after administration of the study intervention) and in which other drugs or chemicals or underlying disease provides plausible explanations (e.g., the participant's clinical condition, other concomitant treatments).

- **Not Related** – The AE is completely independent of study intervention administration, and/or evidence exists that the event is definitely related to another etiology. There must be an alternative, definitive etiology documented by the clinician.

[8.3.3.3 Expectedness](#)

Principal investigator and co-investigators will be responsible for determining whether an adverse event (AE) is expected or unexpected. An AE will be considered unexpected if the nature, severity, or frequency of the event is not consistent with the risk information previously described for the study intervention.

[8.3.4 Time Period and Frequency for Event Assessment and Follow-up](#)

The occurrence of an adverse event (AE) or serious adverse event (SAE) may come to the attention of study personnel during study visits and interviews of a study participant presenting for medical care, or upon review by a study monitor.

All AEs including local and systemic reactions not meeting the criteria for SAEs will be captured on the appropriate case report form (CRF). Information to be collected includes event description, time of onset, clinician's assessment of severity, relationship to study product (assessed only by those with the training and authority to make a diagnosis), and time of resolution/stabilization of the event. All AEs occurring while on study must be documented appropriately regardless of relationship. All AEs will be followed to adequate resolution.

Any medical condition that is present at the time that the participant is screened will be considered as baseline and not reported as an AE. However, if the study participant's condition deteriorates at any time during the study, it will be recorded as an AE.

Changes in the severity of an AE will be documented to allow an assessment of the duration of the event at each level of severity to be performed. AEs characterized as intermittent require documentation of onset and duration of each episode.

PI and co-investigators will record all reportable events with start dates occurring any time after informed consent is obtained until 7 (for non-serious AEs) or 30 days (for SAEs) after the last day of study participation. At each study visit, the investigator will inquire about the occurrence of AE/SAEs since the last visit. Events will be followed for outcome information until resolution or stabilization.

[8.3.5 Adverse Event Reporting](#)

Each investigator is responsible for reporting adverse events to the IRB at their institution, to the Data Coordinating Center (DCC), and to the NIH Program Official. The DCC will summarize the case and report it to the NIDDK program official and the Executive Secretary of the DSMB, who will determine whether it should be shared with the DSMB immediately or reported as part of the next scheduled report to the DSMB. The investigator must promptly inform the Ethics Board or IRB of adverse event per local reporting requirement. The Chair of the DSMB can convene an emergency meeting of the DSMB.

Every six months, or upon request of the NIDDK, the data coordinating center will summarize all adverse events (serious, expected, and unexpected) by treatment group in a report to the DSMB. In addition, the report will contain accrual, drop-out rates, and data quality metrics. The DSMB will summarize their findings to the NIH with a recommendation to continue the clinical trial, modify the trial, or terminate the trial.

[8.3.6 Serious Adverse Event Reporting](#)

The study clinician will immediately report to the sponsor any serious adverse event, whether or not considered study intervention related, including those listed in the protocol and must include an assessment of whether there is a reasonable possibility that the study intervention caused the event. Study endpoints that are serious adverse events (e.g., all-cause mortality) must be reported in accordance with the protocol unless there is evidence suggesting a causal

relationship between the study intervention and the event (e.g., death from anaphylaxis). In that case, the investigator must immediately report the event to the sponsor and the IRB of record.

All serious adverse events (SAEs) will be followed until satisfactory resolution or until the site investigator deems the event to be chronic or the participant is stable. Other supporting documentation of the event may be requested by the Data Coordinating Center/DSMB/NIH and should be provided as soon as possible.

8.3.7 Reporting Events to Participants

Participants will be informed of AEs during an office visit soon after detecting AEs to discuss the problem and treatment options.

Participants will be informed of incidental findings soon after detecting them to discuss the problem and treatment options.

8.3.8 Events of Special Interest

Not applicable

8.3.9 Reporting of Pregnancy

Participants who become pregnant after entering the study will be withdrawn from the study and none of the study procedures will be performed.

8.4 Unanticipated Problems

8.4.1 Definition of Unanticipated Problems (UP)

The Office for Human Research Protections (OHRP) considers unanticipated problems involving risks to participants or others to include, in general, any incident, experience, or outcome that meets all of the following criteria:

- Unexpected in terms of nature, severity, or frequency given (a) the research procedures that are described in the protocol-related documents, such as the Institutional Review Board (IRB)-approved research protocol and informed consent document; and (b) the characteristics of the participant population being studied;
- Related or possibly related to participation in the research (“possibly related” means there is a reasonable possibility that the incident, experience, or outcome may have been caused by the procedures involved in the research); and
- Suggests that the research places participants or others at a greater risk of harm (including physical, psychological, economic, or social harm) than was previously known or recognized.

8.4.2 Unanticipated Problem Reporting

The investigator will report unanticipated problems (UPs) to the reviewing Institutional Review Board (IRB), the NIDDK program official, and to the Data Coordinating Center (DCC)/lead principal investigator (PI). The UP report will include the following information:

- Protocol identifying information: protocol title and number, PI’s name, and the IRB project number;
- A detailed description of the event, incident, experience, or outcome;
- An explanation of the basis for determining that the event, incident, experience, or outcome represents an UP;
- A description of any changes to the protocol or other corrective actions that have been taken or are proposed in response to the UP.

To satisfy the requirement for prompt reporting, UPs will be reported using the following timeline:

- UPs that are serious adverse events (SAEs) will be reported to the IRB and to the DCC/study sponsor within 30 days of the investigator becoming aware of the event.
- Any other UP will be reported to the IRB and to the DCC/study sponsor within 30 days of the investigator becoming aware of the problem.

- All UPs should be reported to appropriate institutional officials (as required by an institution's written reporting procedures), the supporting agency head (or designee), and the Office for Human Research Protections (OHRP) within 30 days of the IRB's receipt of the report of the problem from the investigator.

8.4.3 Reporting Unanticipated Problems to Participants

Participants will be informed of UPs during an office soon after detecting AEs to discuss the problem and treatment options.

9. Statistical Considerations

9.1 Statistical Hypothesis

Primary Aim

We anticipate that patients who received transvaginal sacrospinous rectopexy (TSR) will show significantly greater surgical success comparing to laparoscopic abdominal ventral rectopexy (LAVR) group, and this change is expected to remain at 24 months. TSR will result in superior outcomes over LAVR.

Secondary Aim

We anticipate that rectal hypermobility can be detected via both dynamic imaging, ultrasound and MR defecography. We expect the degree of a rectal support defect will correlate well between the two imaging modalities and with symptom severity.

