1.1 Synopsis

Title:	Prospective Randomized Controlled Trial Comparing Transvaginal Rectopexy and Ventral Mesh Rectopexy for Obstructed Defecation in Pelvic Organ Prolapse (PROD Trial)
Study Description:	This is a collaborative 2-armed multi-center prospective clinical trial comparing: a) transvaginal sacrospinous rectopexy (TSR) with and without conventional vaginal prolapse surgery (CVPS); vs. b) laparoscopic abdominal ventral rectopexy (LAVR) with and without conventional vaginal prolapse surgery (CVPS). Women with vaginal prolapse who report obstructed defecation (OD) symptoms in more than 50% of their bowel movements with significant rectal hypermobility (more than 50% compression ratio in dynamic pelvic ultrasound) will be approached for enrollment. Eligible and consented participants will be randomized to undergo one of the two procedures: 1) laparoscopic abdominal ventral rectopexy with and without CVPS; 2) transvaginal sacrospinous rectopexy with and without CVPS. After the procedure, participants will be followed for 2-week, 2-month, 12-month, and 24-month post-operative visits. Symptom evaluation, pelvic exam, and dynamic pelvic ultrasound completed pre- and post-operatively will be used to compare the outcomes of the two procedures.
Outcomes:	Primary Outcome: Compare surgical success or failure in female participants with moderate to severe OD symptoms, and rectal hypermobility diagnosed by ultrasound, who are randomized to minimally invasive transvaginal sacrospinous rectopexy versus laparoscopic abdominal ventral rectopexy at 24 months after surgery. The primary outcomes will be measured by: 
1. The degree of rectal hypermobility measured via dynamic pelvic ultrasound (i.e. compression ratio). Secondary Outcomes: 
a. Compare efficacy and safety of the surgery.b. Compare the use of dynamic pelvic ultrasound imaging versus MR defecography to measure occult rectal hypermobility.c. Develop and validate a computational finite element model and statistical shape modeling approach to describe the mechanics of normal defecation and the role of rectal and vaginal support deficiencies in causing OD symptoms.
Study Population:	120 participants who are female, between the age of 18 and 80, and who may and may not have vaginal prolapse, who report OD symptoms in more than 50% of their bowel movements and with significant rectal hypermobility
Phase:	N/A

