 3. Global improvement in bladder function – Participants will complete the Patient Global Impression of Improvement (69) at 2, 12 and 24 months postoperatively.
 4. Pelvic Floor Distress Inventory (PFDI) – Prolapse and colorectal symptoms as assessed by the Pelvic Organ Prolapse Distress Inventory (POPDI) and Colorectal Anal Distress Inventory (CRADI) (short-term) and urinary and colorectal symptoms as assessed by the Urinary Distress Inventory (UDI) and CRADI (long-term) subscales at 2, 12, and 24 months postoperatively.
 5. Quality of life measured by Pelvic Floor Impact Questionnaire (PFIQ) (65), Short Form Health Survey (SF-36) (70), EuroQol-5D (EQ-5D) (71) at 2, 12 and 24 months postoperatively. The SF-36 will also be administered to a subset of participants 2 weeks post-operatively to allow validation of the Pain and Activity Assessment Scale.

6. Pelvic muscle strength measured by the Brink Scale at 2, 12, and 24 months postoperatively (72).

- Compare the use of posterior compartment dynamic pelvic ultrasound imaging versus MR defecography to measure occult rectal hypermobility.
- Develop and validate a computational finite element model and statistical shape modeling approach to describe the mechanics of normal defecation and the role of rectal and vaginal support deficiencies in causing OD symptoms.

4. Study Design

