5.1 Inclusion Criteria

In order to be eligible to participate in this study, an individual must meet all of the following criteria:

1. Female, between the age of 18 and 80
2. OD symptoms as indicated by an affirmative response to either questions 7, 8 or 14 of the Pelvic Floor Distress Inventory (PFDI):
 - a. Do you feel you need to strain too hard to have a bowel movement?
 - b. Do you feel you have not completely emptied your bowels at the end of a bowel movement?
 - c. Does part of your bowel ever pass through the rectum and bulge outside during or after a bowel movement?
3. Rectal hypermobility defined as a compression ratio greater than 50% according to ultrasound
4. Patient planning on undergoing surgery for the repair of pelvic organ prolapse within the next 12 months
5. Patient who is not pregnant and does not intend to become pregnant in the next 2 years
6. Available for 24-months of follow-up
7. Stated willingness to comply with all study procedures and availability for the duration of the study
8. Able to complete study assessments, per clinician judgment
9. Able and willing to provide independent written informed consent

10. Stable cardiovascular and respiratory status to meet candidacy in vaginal or laparoscopic surgeries

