9.4.3 Analysis of the Secondary Endpoint(s)

Subjective Surgical Outcome

The secondary endpoint is the presence of OD symptoms (yes/no) at 24 months after surgery. Questionnaires that assess the presence and severity of OD symptoms include pain/activity assessment scale, global improvement in bladder function, prolapse and colorectal symptoms as assessed by POPDI, CRADI, UDI, quality of life by PFIQ, SF-36, EQ-5D, and pelvic muscle strength measured by Brink Scale. Differences between surgical treatments will be analyzed using generalized linear mixed-effects models, as described for the primary endpoint. However, imputation of missing values will not be done for secondary measures.

Validation

There will be two forms of validation: statistical and radiological. For statistical validation, we expect to see a significant and positive correlation between measurements of the Compression ratio between the two modalities. However, since the Compression ratio as measured via MR defecography is not used clinically to diagnose abnormalities in rectal support (rectal prolapse or rectal intussusception), this does not validate the use of ultrasound for diagnostic purposes. Thus, radiological validation will be performed where the Compression ratio is also correlated with a radiologist's diagnosis of an abnormality in rectal support.

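### Entry requires an ultrasound compression ratio above 50%, so detection by ultrasound cannot fail as a hypothesis, ultrasound specificity and negative predictive value cannot be estimated, and the planned correlations are attenuated

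*Combined protocol and SAP*

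**What the plan says.** - **Eligibility.** Section 5.1 says "an individual must meet all of the following criteria", and criterion 3 is "Rectal hypermobility defined as a compression ratio greater than 50% according to ultrasound". Criterion 2 also makes symptoms a condition of entry: "OD symptoms as indicated by an affirmative response to either questions 7, 8 or 14" of the PFDI.
- **Timing.** In the Schedule of Activities (1.3), ultrasound is done at screening and at 2, 12 and 24 months. MR defecography is done once, at its own visit after screening and before randomization. Only the baseline ultrasound has a paired MR. No group of ultrasound-negative women is described.
- **Aim.** The Synopsis lists as a secondary outcome: "Compare the use of dynamic pelvic ultrasound imaging versus MR defecography to measure occult rectal hypermobility". Section 3 repeats it with slightly different wording. Neither names a metric.
- **Hypothesis.** Section 9.1 has two parts. The first is detection: "We anticipate that rectal hypermobility can be detected via both dynamic imaging, ultrasound and MR defecography". The second is correlation: "We expect the degree of a rectal support defect will correlate well between the two imaging modalities and with symptom severity".
- **Analysis.** Section 9.4.3 plans a correlation of the two compression ratios. It concedes that this does not validate ultrasound as a diagnostic test, and adds that "radiological validation will be performed where the Compression ratio is also correlated with a radiologist's diagnosis of an abnormality in rectal support". Section 9.4.9 plans a ROC cut-off, with sensitivity and specificity, for the presence of OD symptoms.
- **Not given.** Appendix A defines an MR compression ratio but no MR cut-off. There is no sample size or target correlation for this aim.

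**The concern.** The sample is selected on the result of the test under study. If every woman is ultrasound-positive on entry, observing that ultrasound detects hypermobility in this sample says nothing about how well it detects it. The step that 9.4.3 relies on for diagnostic validation, comparison with the radiologist's diagnosis, uses the same selected women. Women whom ultrasound would have called negative, rightly or wrongly, are never scanned by MR.

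The risk is a misread result. Sections 2.1 and 4.2 report from earlier work that ultrasound seemed to make MR unnecessary and seemed superior to it. A detection rate of 100% could be taken to confirm this, although this sample cannot test it. In the other direction, a modest correlation produced by selection could be taken as evidence that ultrasound and MR agree poorly.

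**Working it through.** The plan states no figure for this aim, so there is none to reproduce.

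**Step 1. The table at the 50% criterion.** Cross the entry ultrasound reading (above 50%, or not) with the radiologist's diagnosis (abnormal, or normal). Let *a* and *b* be the numbers of ultrasound-positive women with an abnormal and a normal diagnosis. The ultrasound-negative row is 0 and 0.

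- Sensitivity = a/(a + 0) = 100%, whatever the true value.
- Specificity = 0/(b + 0) = 0%, which is forced and so estimates nothing.
- Negative predictive value = 0/0, undefined.
- Positive predictive value = a/(a + b). This can be estimated.

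One qualification: 6.3 and Appendix B provide a blinded re-read of stored images, which could put a few women at or below 50%. These would be borderline reading differences, not a sampled negative group.

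**Step 2. What selection does to the planned correlations.** Inputs: pre-operative ultrasound ratio 45.5 ± 18.4 from the earlier case series (4.2) and the entry cut-off of 50 (5.1). Assumptions: normality, the same mean and SD on MR, and a pre-selection correlation r of 0.5 to 0.9.

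- Standardised cut-off: z = (50 − 45.5)/18.4 = 0.245.
- Proportion above it: 0.403. Normal density at z: 0.387. Ratio λ = 0.387/0.403 = 0.960.
- Mean ultrasound ratio among enrolled women: 45.5 + 18.4 × 0.960 = 63.2.
- Variance ratio: v = 1 + zλ − λ² = 1 + 0.235 − 0.921 = 0.313.
- SD among enrolled women: 18.4 × √0.313 = 10.3.
- Correlation after selection: r√v / √(1 − r² + r²v). For r = 0.7: 0.392/√(0.51 + 0.154) = 0.48.

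| r before selection | r after selection | MR ratio above 50% among enrolled women |
|---|---|---|
| 0.5 | 0.31 | 60% |
| 0.7 | 0.48 | 70% |
| 0.9 | 0.76 | 83% |

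The last column assumes an MR cut-off of 50%, which the plan does not set. The ultrasound figure beside it would be 100% in every row.

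**Step 3. Correlation with the radiologist's diagnosis.** Section 9.4.3 does not say which modality's ratio is meant; since the purpose is to validate ultrasound, it is read here as the ultrasound ratio. A simulation of 1,000,000 women treated ultrasound, MR and the diagnosis as equally good measures of one underlying defect, with the same mean, SD and cut-off as in step 2.

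| Reliability | Either modality, unselected | Ultrasound, enrolled | MR, enrolled |
|---|---|---|---|
| 0.6 | 0.47 | 0.27 | 0.36 |
| 0.7 | 0.55 | 0.32 | 0.40 |
| 0.8 | 0.63 | 0.35 | 0.43 |
| 0.9 | 0.71 | 0.36 | 0.44 |

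The area under the ROC curve against the diagnosis behaves in the same way: equal before selection (0.78 to 0.94), then 0.67 to 0.82 for ultrasound and 0.72 to 0.85 for MR.

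**Step 4. If detection rates were compared.** Suppose both methods have 80% sensitivity with independent errors, all 120 women truly have the defect, and all have a complete MR. Then about 120 × 0.2 = 24 women are positive on ultrasound only and none on MR only. The exact McNemar p is 2 × 0.5^24, about 1 × 10⁻⁷. At 90% sensitivity the split is 12 to 0, and p = 2 × 0.5^12 = 0.0005. Two equally sensitive methods would be declared different. The plan contains no such test.

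**The case against.** The best defence is that the plan does not do what would be most misleading. It contains no paired test of detection and no MR cut-off. Section 9.4.3 already says that agreement between modalities is not diagnostic validation. The compression ratio is continuous and still varies above 50%, so the planned correlations can be computed. The superiority and replacement statements in 2.1 and 4.2 describe earlier work, and no analysis here tests them.

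Most of this stands, and it limits the point. A reader might infer that the radiological validation will make ultrasound look better than MR. The documents do not support that: the validation is written as a correlation, and step 3 shows that selection on ultrasound then makes it look worse than an equally good MR. A reader might also infer that the whole secondary hypothesis is true by construction. Only the ultrasound half of the detection part is; the correlation part can fail. The McNemar figures in step 4 belong to an unplanned test. They also assume no ultrasound false positives and 120 complete MR scans, although 7.1 lets a woman continue with incomplete MR.

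The defence does not restore the detection hypothesis, and it does not supply ultrasound-negative women. The concession in 9.4.3 also makes the radiological validation carry the diagnostic claim, which this sample cannot support at the 50% criterion.

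**Conclusion.** The point holds in a limited form. Three conclusions follow:

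1. Apart from possible re-reads, detection by ultrasound is 100% among enrolled women, so it cannot serve as a hypothesis.
2. At the 50% criterion, ultrasound specificity and negative predictive value cannot be estimated, and sensitivity is fixed by design. This and the first conclusion follow from eligibility and scheduling alone and need no modelling.
3. The planned correlations are attenuated, to the disadvantage of ultrasound: for illustration, from 0.7 to about 0.48. The size rests on normality, on equal distributions for the two modalities and on borrowing the earlier series' mean and SD. The women screened for this trial may be distributed differently. Under normality, truncation always reduces the spread, so the direction does not depend on those values.

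Selection thus pushes a detection rate up and a correlation down, and neither answers whether ultrasound is a valid diagnostic test. This affects a secondary aim; the randomized comparison of the two operations is untouched.

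**What to change.** - **Section 9.1.** Remove detection by ultrasound as a hypothesis. State the aim as estimating, among women with an ultrasound compression ratio above 50%, the proportion with abnormal rectal support on the radiologist's MR reading, with a 95% interval. This is a positive predictive value.
- **Section 9.4.3.** State that the correlations apply only to ultrasound-positive women and are range-restricted. State that no ultrasound sensitivity, specificity or negative predictive value for rectal support defects, and no claim that ultrasound is superior to MR or can replace it, will be drawn from this sample.
- **Section 9.4.9.** Make the planned sensitivity and specificity consistent with this. They refer to OD symptoms, not to rectal support defects, so the text should say so and name the modality and visit. Symptoms are themselves an entry criterion, so the paired baseline data contain no symptom-free women.

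The data are already being collected and no scans are added. As a guide to precision, if 80% of 120 women had an abnormal reading, the half-width of the interval would be about 1.96 × √(0.8 × 0.2/120) = 0.07; at 50% it would be 1.96 × √(0.25/120) = 0.09. Both proportions are assumptions, and incomplete MR would widen the interval. The downside is a narrower diagnostic claim. A broader one would need MR, read blind to ultrasound, in symptomatic women screened at 50% or below, with an MR cut-off fixed in advance; that does add scans.
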